7.2. Subject Exclusion Criteria

Subjects are excluded from this study if any 1 or more of the following criteria is met:

1. Subject has clinically atypical and /or rapidly growing Seborrheic Keratoses.
2. Subject has presence of multiple eruptive Seborrheic Keratoses (Sign of Lesser -Trelat).
3. Subject has current systemic malignancy.
4. Subjects have previously received A-101 (hydrogen peroxide) Topical Solution, 40% treatment.
5. Subject has used any of the following therapies within the specified period prior to Visit 2 on, or in a proximity to any target or non-target SK, that in the investigator's opinion interferes with the study medication treatment or the study assessments:
 - a. LASER, light or other energy-based therapy (*e.g.*, intense pulsed light [IPL], photodynamic therapy [PDT]); 30 days
 - b. Imiquimod, 5-fluorouracil (5FU), or ingenol mebutate; 60 days
 - c. Retinoids; 28 days
 - d. Microdermabrasion or superficial chemical peels; 14 days
6. Subject would require the use of any topical treatment (*e.g.*, moisturizers, sunscreens) to any of the target or non-target SKs 12 hours prior to any study visit.
7. Subject currently has or has had any of the following within the specified period prior to Visit 1 on or in a proximity to any target or non-target SK that, in the investigator's opinion, interferes with the study medication treatment or the study assessments:
 - a. Cutaneous malignancy; 180 days
 - b. Sunburn; currently
 - c. Pre-malignancy (*e.g.*, actinic keratosis); currently
 - d. Body art (*e.g.*, tattoos, piercing, etc.); currently
 - e. Excessive tan; use of self-tanning lotions/sprays is prohibited
8. Subject has a history of sensitivity to any of the ingredients in the study medications.
9. Subject has any current skin disease (*e.g.*, psoriasis, atopic dermatitis, eczema, sun damage), or condition (*e.g.*, sunburn, excessive hair, open wounds) that, in the opinion of the investigator, might put the subject at undue risk by study participation or interfere with the study conduct or evaluations.
10. Participation in another therapeutic investigational drug trial in which administration of an investigational study medication occurred within 30 days prior to Visit 1.

7.3. Subject Withdrawal Criteria

A subject may be removed from the study therapy for a variety of reasons, including:

- Unacceptable adverse event.
- Subject unwilling or refusal to continue with the protocol defined study visits and/or consent withdrawal for study participation.
- Change in compliance with an inclusion/exclusion criterion.

- Use of a prohibited medication during the treatment period.
- General or specific changes in the subject's condition that render the subject unacceptable for further treatment in this study in the judgement of the investigator.

If a subject is to be withdrawn from the study, the Aclaris Therapeutics, Inc. study monitor, or designee, must be informed with 24 hours of the decision to remove the subject from the study.

The study may be discontinued at the discretion of Aclaris Therapeutics, Inc. Some examples of reasons for discontinuation are the occurrence of the following:

- Increased frequency, severity or duration of known AEs
- Medical, regulatory or ethical reasons affecting the continued performance of the study
- Difficulties in the recruitment of subjects.

7.4. Withdrawal Procedures

If a subject withdraws from the study prior to Visit 11, the reason for and the date of withdrawal from the study must be recorded on the eCRF. If the reason for withdrawal is an adverse event, monitoring of the subject will continue until the event has resolved or stabilized, until the subject is referred to the care of a local health care professional, or until a determination of a cause unrelated to the study drug or study procedure is made.

7.5. Subject Replacement

If a subject is enrolled to the study but does not receive a dose of study drug, then the subject may be replaced.

Subjects that are determined to be screen failures may be rescreened for the study and if determined to be eligible for the study they may be enrolled using the same subject identifier and must sign a new informed consent form.

7.6. Subject Identifier (SI)

The investigator or designee will assign a unique five-digit subject identifier (SI) to each subject at Visit 1.

The SI format will be NN-NNN where the first 2 digits are the investigational center site number (using leading zeroes, as appropriate). The final 3 digits are the subject number and must be assigned in ascending numerical order, without omitting or repeating any number, starting with 001 at each investigational center. For example, the SI for the second subject that signs an informed consent at site number 04 would be 04-002.

The subject will be identified using the SI in all study documentation for the duration of the study.

8. TREATMENT OF SUBJECTS

8.1. Description of Study Drug

Table 4: Investigational Product

	Investigational Product
Product Name:	A-101 (Hydrogen Peroxide) Topical Solution, 40% (w/w)
A-101 Concentration (%):	Hydrogen peroxide 40% (w/w)
Pharmaceutical Form	Solution
Route of Administration	Topical
Manufacturer	James Alexander Corporation, Blairstown NJ
Storage Conditions	Room temperature: 59°F to 77°F (15°C to 25°C) protected from excessive heat, open flame and combustibles, out of direct sunlight and in a well-ventilated, dry area. Excursions from these conditions must be reported to Aclaris Therapeutics, Inc.
Application	Nitrile or vinyl examination gloves must be worn during the application process. Latex gloves are prohibited.
Duration of Administration	Apply study medication to each target and non-target SK for approximately 20 seconds, then allow each target and non-target SK to remain undisturbed for approximately 60 seconds. Repeat the application/waiting cycle until the A-101 40% has been applied to each target and non-target SK up to 4 times. Subjects may receive up to 3 treatments. (Visit 2, Visit 5 and Visit 7)
Activated Applicators	Activated applicators are stable for 4 hours at room temperature 59°F to 77°F (15°C to 25°C)

8.2. Previous Therapies

During Visit 1, the investigator or designee will question the subject to ensure they have not used any excluded therapies (Section 8.4).

8.3. Concomitant Medications

Concomitant therapies are any new or existing therapy received from Visit 1 until discharge from the study.

Concomitant therapies include drug (*e.g.*, prescription, over-the-counter [OTC]) and non-drug (*e.g.*, chiropractic, physical therapy, energy-based treatments) therapies. Subjects will refrain from receipt of any therapy in compliance with the inclusion/exclusion criteria.

All new or modified concomitant therapies used during the study must be recorded in the subject CRF.

8.4. Prohibited Therapies

During the course of this study, subjects are prohibited from using the following treatment therapies to treat any of the target and non-target SKs:

- Retinoids (topical)
- Corticosteroids (topical)
- LASER, light or other energy-based therapy
- Liquid nitrogen, electrodesiccation, curettage, imiquimod, ingenol mebutate
- Microdermabrasion or superficial chemical peels
- Antibiotics (topical)
- Self-tanner lotions and sprays

The investigator should notify the Medical Monitor immediately if any prohibited therapies are required to ensure subject safety.

Starting with Visit 2, subjects must not apply any topical products (*e.g.*, moisturizers, sunscreens, etc.) to their target and non-target SK within 12 hours prior to any study visit (Note: routine cleansing products are allowed).

After the completion of any study visit where a study medication treatment was performed subjects must NOT wash/submerge the target or non-target SK for at least 6 hours and must not apply any topical products to the target or non-target SK for at least 6 hours.

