⁴Vital signs [including temperature, pulse, respiratory rate, blood pressure, height and weight (Visit 1 only)] will be measured by a qualified staff member at Visit 1, Visit 2, Visit 5, Visit 7, Visit 10, and Visit 11.

⁵Prior medications/therapies will be collected for a time-period of 13 days prior to Visit 1. Refer to Section 8.4 for a list of permitted and restricted concomitant medications.

⁶The treating investigator will identify 3 target SKs and up to 4 non-target SKs. Two (2) target SKs must be on the face, and the additional 1 target SK must be on the neck or décolletage. The 4 non-target SKs may be located on the face, neck, or décolletage.

⁷The investigator will use the Physician's Lesion Assessment (PLA) to assess the severity of each target and non-target SKs at Visits 1, 2, 3, 4, 5, 7, 10, and 11. At Visit 2, Visit 5 and Visit 7, the investigator must assess each target and non-target SK prior to application of the study medication. In order to be eligible for enrollment to the study during Visit 2, the subject must have a PLA grade ≥ 2 for each target and non-target SK.

⁸The investigator will measure the dimensions of each target and non-target SK at Visits 1, 2, 3, 4, 5, 7, 10 and 11. At Visit 2, Visit 5 and Visit 7, the investigator must measure each target and non-target SK prior to application of the study medication. In order to be eligible for enrollment to the study during Visits 1 and 2, each target SK must have a diameter that is between ≥ 5 and ≤ 15 mm (inclusive) and be raised. In order to be eligible for enrollment to the study during Visits 1 and 2, each non-target SK must be a raised SK. At Visits 3, 4, 5, 7, and 10 the investigator must assess the thickness of each target and non-target SK above the surrounding skin. Additional target and non-target SK requirements are outlined in Section 10.1 .

⁹Each target and non-target SK will be photographed at all study visits using the Aclaris Therapeutics, Inc. supplied photography equipment.

¹⁰During Visit 2 each target and non-target SK will be photographed prior to the application of A-101 40%, 10 minutes post application (+2 minutes), and 1-hour post application (± 10 minutes). During Visit 5 and Visit 7, the target and non-target SKs will be photographed prior to the application of A-101 40%, if applicable.

¹¹During Visit 3 each target and non-target SK will be photographed 24-hours post application during Visit 2 (± 2 hours).

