14.2. Protocol Deviations, Violations, and Exceptions

A protocol **deviation** is non-adherence to protocol-specific study procedures or schedules that does not involve inclusion/exclusion criteria, primary objective variable criteria, and/or GCP guidelines. Deviations are considered minor and do not impact the study.

A protocol **violation** is defined as any divergence from the protocol-specific inclusion/exclusion criteria, subject is administered a prohibited medication during the active protocol treatment period, primary objective variable criteria, and/or GCP guidelines. Protocol violations will be identified and recorded, by study center personnel, on the CRF.

As a matter of policy, sponsor/CRO will not grant **exceptions** to protocol-specific entry criteria to allow subjects to enter a study. If under extraordinary circumstances such action is considered ethically, medically, and scientifically justified for a particular subject, prior approval from sponsor/CRO and the responsible IRB/IEC, in accordance with the Sponsor/CROs Standard Operating Procedure (SOP), is required before the subject will be allowed to enter the study. If investigative center personnel learn that a subject who did not meet protocol eligibility criteria was entered in a study (a protocol violation), they must immediately inform sponsor/CRO. Such subjects will be discontinued from the study, except in a rare instance following review and written approval by sponsor/CRO and the responsible IRB/IEC, according to the applicable SOP

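### SAP 3.5 stops counting new medications before both endpoint visits and omits non-drug therapies, and Protocol 8.4 does not clearly keep exclusion 5's proximity rule or 5FU in force after Visit 2

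*Protocol*

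**What the plan says.** **Collection and tabulation.** Protocol 8.3 defines concomitant therapy as drug and non-drug, from Visit 1 to discharge. Table 3 footnote 14 requires both on the CRF. SAP 1.1.3 names concomitant medication use among the safety assessments. SAP 3.5 summarizes medications by ATC class and preferred term. It calls a medication prior if taken before the first treatment, and concomitant if taken from the first application to 30 days past the last. It plans no summary of non-drug therapies.

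**On-study rule.** Protocol 8.4 applies throughout the study and states that "subjects are prohibited from using the following treatment therapies to treat any of the target and non-target SKs". Imiquimod and ingenol mebutate are on its list; 5FU is not.

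**Entry rule.** Exclusion 5 in Protocol 7.2 begins "Subject has used any of the following therapies within the specified period prior to Visit 2 on, or in a proximity to any target" and extends to non-target SKs, where the investigator judges that the use interferes. Item 5b reads "Imiquimod, 5-fluorouracil (5FU), or ingenol mebutate; 60 days".

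**Enforcement.** Protocol 8.3 asks subjects to refrain from therapies in line with the eligibility criteria. Section 7.3 gives as possible grounds for removal "Change in compliance with an inclusion/exclusion criterion" and "Use of a prohibited medication during the treatment period". Section 14.2 treats departures from the eligibility criteria as violations, and also the case where "subject is administered a prohibited medication during the active protocol treatment period". Table 3 footnote 5 points the site to 8.4: "Refer to Section 8.4 for a list of permitted and restricted concomitant medications".

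**The concern.** The study has one arm, so any change in a treated lesion will be read as the result of A-101. A laser session, peel, retinoid or 5FU course beside a study SK, given for another reason, could clear or irritate that SK. Clearance would move PLA, a secondary endpoint. Irritation could move the subject's rating of the treated skin (end-of-study items 4 and 8) without moving PLA, because the PLA manual still grades a site 0 when erythema, roughness or scaling remains. That would blur the planned PLA-satisfaction relation. No PLA is scheduled between Day 29 and Day 85, so the scores would not show when a lesion changed.

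A reader would look to the concomitant-therapy table to rule this out. As SAP 3.5 stands, that table cannot show a medication begun in the weeks before either endpoint visit, or any procedure at all. It would also miss a medication started to treat a late adverse event, although non-serious events are recorded to Visit 11.

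**Working it through.** **Step 1. Timeline check.** The protocol gives a maximum participation of 134 days. Screening runs from Day -13 to Day 0 (14 days), then 113 days, then a 7-day window: 14 + 113 + 7 = 134. The day numbering agrees.

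**Step 2. Where SAP 3.5 stops.** Treatment visits are Visit 2 (Day 1), Visit 5 (Day 15, ±1) and Visit 7 (Day 29, ±1). Retreatment applies only to lesions with PLA of at least 1, and a subject who refuses it may stay in the study, so any of the three can be the last. Cut-off = last application day + 30. Gap = endpoint day − cut-off.

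| Last application | Cut-off | Gap to Day 85 | Gap to Day 113 |
|---|---|---|---|
| Visit 2, Day 1 | 1 + 30 = 31 | 85 − 31 = 54 | 113 − 31 = 82 |
| Visit 5, Day 15 | 15 + 30 = 45 | 85 − 45 = 40 | 113 − 45 = 68 |
| Visit 7, Day 29 | 29 + 30 = 59 | 85 − 59 = 26 | 113 − 59 = 54 |

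**Step 3. Window limits.** Visit 10 and Visit 11 are each ±7 days. Smallest gap: Visit 7 on Day 30 gives a cut-off of Day 60; the earliest Visit 10 is Day 78; 78 − 60 = 18 days. Largest gap: cut-off Day 31 and the latest Visit 11 on Day 120; 120 − 31 = 89 days. The cut-off therefore always precedes both endpoint visits. Counting to Visit 11 would bring the gap to zero.

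**Step 4. What the gap covers.** SAP 3.5 counts a medication taken at any time in its window, so one begun earlier and continued is still counted. The gap applies to new starts only. Non-drug therapies are outside the table at all times.

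**Step 5. The two therapy rules side by side.**

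| | Exclusion 5 | Section 8.4 |
|---|---|---|
| Period | Stated intervals before Visit 2 | Course of the study |
| Reach | On or near a study SK | Used as treatment of a study SK |
| Condition | Investigator judges interference | None |
| 5FU | Named | Absent |
| Cryotherapy, electrodesiccation, curettage, topical corticosteroids, topical antibiotics, self-tanners | Absent | Named |

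Section 8.4 is the broader list in its last row and the narrower one in reach and on 5FU. Listing self-tanners, which treat no SK, suggests that use on the lesion was meant whatever the purpose. That reading still leaves out use nearby.

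**The case against.** **The eligibility rules may already carry over.** Section 8.3 is an on-study section and tells subjects to refrain in line with the eligibility criteria; 7.3 and 14.2 also act on those criteria. The natural purpose of such sentences is to keep exclusion 5 alive. This stands in part. A reader might infer that therapy beside a study SK is plainly allowed after Visit 2, and the documents do not support that. But exclusion 5 is dated back from Visit 2, so a peel on Day 60 breaches none of its words. The carry-over is arguable, not clear.

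**The treatment period may mean the whole study.** The synopsis and SAP 2.3.4 give total participation under the heading of treatment duration. SAP 3.6 instead counts from first to last application. So one cannot say that the 7.3 and 14.2 clauses lapse at Visit 7, only that the period is undefined. Both clauses also speak of a medication, which does not clearly include laser or peels.

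**Subject instructions.** Section 10.2 tells subjects to continue routine skin care, and one might infer that self-tanners are its only exception. That is wrong: it also limits UV exposure and bars topical products on study SKs for 12 hours before visits and 6 hours after treatment. The instruction sheet itself (Appendix 1) was not in the text available.

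**Other safeguards.** Exclusion 7 removes subjects with interfering actinic keratosis or recent skin cancer near a study SK, which reduces reasons for 5FU there. Therapies are recorded and lesions photographed at every visit, and 11.3.1 requires questions about confounders for SK-related events. These make the problem less likely and partly recoverable.

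**The SAP point concerns reporting, not collection.** This is correct. The data are on the CRF, the SAP describes no listings for any domain, and its 30-day limit matches the adverse-event window in SAP 3.8.1. None of this reconciles SAP 3.5 with Protocol 8.3.

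**Conclusion.** Both points hold as inconsistencies in the stated rules. The firmer one is in the SAP: its cut-off falls at Day 31, 45 or 59 (Day 60 at the window limit), at least 18 days before Visit 10 and nominally 54 to 82 days before Day 113, while the protocol collects until discharge. Medications first started in that interval belong to neither category, and non-drug therapies have no planned summary. The second is an ambiguity: 8.4 is narrower than exclusion 5 in reach and on 5FU, and 8.3 and 7.3 do not clearly close the difference.

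A reader might go further and infer that clearance or satisfaction will be inflated by some calculable amount. The documents give no rate of such therapy use and no basis for assuming how many lesions it would clear, so the bias is unknown and may be zero. A reader might also infer that the therapies go unrecorded, which is not so.

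The conclusion assumes that the last application in SAP 3.5 means each subject's own last application. It is limited to this SAP: a separate plan for satisfaction and its relation to PLA is announced in SAP section 3 but was not available. Overall, this is a minor improvement worth making because it costs little.

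**What to change.** **SAP 3.5.** Count concomitant medications through Visit 11. Add a listing of non-drug therapies and procedures on the face, neck and décolletage, drawn from the existing CRF. This needs only minor programming and no new data, and can be done without a protocol amendment.

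**Protocol.** Reword 8.4 to prohibit its listed therapies plus 5FU, on or near any target or non-target SK, from Visit 2 through Visit 11, whatever the purpose. Keep the existing route of notifying the Medical Monitor when such a therapy is needed for safety. Use the same term (prohibited therapy) and the same period (through Visit 11) in 7.3 and 14.2. In 10.2, except the 8.4 list from the advice to continue routine products, and conform the subject instruction sheet if needed. Cosmetic care away from study SKs need not be restricted.

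The cost is one amendment with IRB approval under 14.1. A subject might also have to delay a listed therapy near a study SK until after Visit 11.

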8.5. Study Medication Treatment

A-101 40% is for external, topical use on the target or non-target SK on the appropriate study subject only.

The Principal Investigator or physician Sub-Investigator performing the A-101 40% treatments must comply with the A-101 40% storage conditions outlined in Section 8.1.

At Visit 2, and Visit 5 and Visit 7 if applicable, each target and non-target SK must be treated by a study trained healthcare provider at the site.

[figure not shown]
At Visit 5 and Visit 7, all identified target and non-target SKs that have a PLA grade of ≥ 1 will be re-treated with A-101 40%. If in the investigator's opinion, the lesion is not appropriate for re-treatment (*e.g.* cutaneous AE) treatment will be withheld. The reason for withholding treatment will be documented in the comment section of the subject's CRF and the AE CRF if appropriate.

8.5.1. Preparing the Study Medication for Application

To perform a study medication treatment for a target or non-target SK a HCP at the site will select the appropriate A-101 40% applicator. The following instructions outline the procedure for application of A-101 40% to the target or non-target SK:

- Prepare for the treatment:
 - Wash your hands prior to, and after completing the A-101 40% treatments
 - Wear nitrile or vinyl examination gloves during the treatment; *latex gloves are prohibited*
 - Select the applicator
 - Visually inspect the applicator for damage:
 - If the applicator appears damaged do not use it for the treatment, contact the study monitor for return/disposal instructions and select an unused applicator for the treatment
 - If the applicator is intact, proceed with the treatment process as outlined in Figure 1

Figure 1: Diagram Showing the Process for Preparing and Applying A-101 40%

1. Each target and non-target SK should be cleaned using an alcohol wipe prior to application of A-101 40%.
2. Hold the A-101 40% applicator so that the applicator cap is pointing up.
3. Crush the ampule in the applicator by applying pressure to the center of the barrel of the applicator.
4. Remove the sleeve.
5. Tap the barrel of the applicator to ensure the solution is free of the crushed ampule.
6. Gently remove the cap by twisting while pulling away from the applicator.
7. Express a single drop of A-101 40% so that the tip of the applicator becomes wet.
8. Apply the solution to the target or non-target SK in a circular motion.

8.5.2. Applying A-101 40% to the Face, Neck or Décolletage

To apply A-101 40% to the target or non-target SK the HCP will follow these treatment instructions:

- Do not apply A-101 40% to eyes, mouth, mucous membranes, open wounds

- Do not apply A-101 40% to the eyelids or within 5 mm of the orbital rim
- If, in the investigator's opinion it is needed to ensure no A-101 40% enters the eye:
 - Position the subject in the supine position with the head slightly elevated and angled such that any excess study medication will flow away from the eye.
 - Apply white petrolatum (100%) United States Pharmacopeia (USP) that is to be applied along the orbital rim and at the medial and lateral canthi; gently stretch the periorbital skin between the thumb and forefinger at the time of petrolatum application to distend any periorbital rhytides (*e.g.*, "crow's feet") and ensure full coverage of the skin at the base of the rhytides to decrease the likelihood of tracking of the study medication towards the eye
 - Have the subject hold an absorbent pad in the appropriate area of the eye to absorb any excess study medication that might track away from the target or non-target SK
 - Instruct the subject to keep both eyes closed during the entire study medication treatment procedure
- After the subject is properly prepared and positioned, thoroughly cleanse the target or non-target SK by firmly rubbing with a swab/wipe wetted with 70% isopropyl alcohol
- Using firm pressure, squeezing in the middle of the applicator, apply one drop of study medication onto the target or non-target SK and then move applicator around in a circular motion to fully saturate the SK. Apply the study medication for approximately 20 seconds
- Minimize exposure to the surrounding normal skin
- During the treatment process remove excess study medication from the surrounding skin using a clean absorbent wipe
- Ensure the target or non-target SK is wet with study medication at the end of the approximately 20 second application
- Allow the target or non-target SK to remain undisturbed for approximately 60 seconds
- After approximately 60 seconds repeat the approximately 20 second application process

Repeat the application/waiting cycle until the study medication has been applied to each target or non-target SK up to 4 times. It is acceptable to treat the target and non-target SKs sequentially to minimize treatment time; such that, after treatment is applied to the 3rd SK, the 60 second wait time between applications would be met.

Record the time the final treatment is completed for the last treated target or non-target SK as the Treatment Completion Time.

